12.3.9 Analysis of safety

The analyses of safety will be based on the safety analysis set. The reporting of safety data will be presented separately for initial treatment and continuation treatment.

12.3.9.1 Adverse events

To assess the safety of tralokinumab in combination with TCS when used to treat moderate-to-severe AD for 32 weeks, the frequency of AEs and SAEs are included as additional secondary endpoints.

AEs will be coded during the course of the trial according to Medical Dictionary for Regulatory Activities (MedDRA). AEs will be presented by preferred terms and primary system organ class (SOC).

Treatment-emergent AEs will be summarised, however, all AEs recorded during the course of the trial will be included in the subject data listings. An event will be considered treatment-emergent if started after the first use of IMP or if started before the first use of IMP (applicable if subject had a wash-out) and worsened in severity thereafter. The tabulations described in the following will only include the treatment-emergent events. In each of the tabulations, AEs will be defined by MedDRA preferred terms within primary SOC.

An overall summary of the number of treatment-emergent AEs and the number (percentage) of subjects with any treatment-emergent AEs, deaths, SAEs, premature discontinuations from the trial due to AEs, treatment-related AEs and severe AEs will be presented.

The number of AEs and the number of subjects experiencing each type of AE will be tabulated by treatment group. The percentage of subjects with AEs in the initial treatment period will be compared between treatment groups by a chi-square test or Fisher's exact test (if expected cell count <5).

Trial ID: LP0162-1339	Date: 29-Aug-2018	Version: 4.0
		Page 100 of 129

The severity for each type of AE will be tabulated by treatment group.

The causal relationship to IMP and NIMP (TCS) for each type of AE will be tabulated by treatment group.

Related AEs are defined as AEs for which the investigator has not described the causal relationship to IMP as 'not related'. The number of related AEs and the number of subjects experiencing each type of related AE will be tabulated. The percentage of subjects with related AEs in the initial treatment period will be compared between treatment groups by a chi-square test or Fisher's exact test (if expected cell count <5).

SAEs and AESIs will be evaluated separately. A narrative for each SAE will be given. AESIs and AEs leading to withdrawal from trial or permanent discontinuation of IMP will be tabulated and listed.

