9.2 Treatment assignment

Subjects who have been found to comply with all the inclusion criteria and not to violate any of the exclusion criteria will be randomised at baseline (Day 0) to receive treatment with either tralokinumab or placebo. Treatment assignment will be pre-planned according to a computer-generated randomisation schedule in a 2:1 ratio (tralokinumab:placebo) stratified by region (Europe and North America) and baseline disease severity (IGA of 3 or 4).

Trial ID: LP0162-1339	Date: 29-Aug-2018	Version: 4.0
		Page 51 of 129

Subjects will be re-randomised to continuation treatment at Week 16. The treatment during this period will depend on the regimen received in the initial treatment period and the subject's clinical response at Week 16. Subjects randomised to tralokinumab who have a clinical response at Week 16 (i.e. IGA 0/1 or EASI75), will be re-randomised to the continuation treatment period in a 1:1 ratio (tralokinumab Q2W:tralokinumab Q4W) stratified by region and IGA response at Week 16 (IGA 0/1 or IGA >1). Subjects randomised to placebo who have a clinical response at Week 16 will continue on placebo. Subjects in either the tralokinumab or placebo group who have not achieved a clinical response at Week 16 will receive tralokinumab Q2W in the continuation treatment period.

IWRS will be used to control randomisation, re-randomisation, and stratification factors, along with IMP supply chain and expiry tracking, and for dispensing and return of NIMP (TCS).

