12.1 Sample size

A total of 369 subjects will be randomised 2:1 to initial treatment in this trial (246 subjects in the tralokinumab+TCS arm; 123 subjects in the placebo+TCS arm).

The primary endpoints for initial treatment, IGA 0/1 and EASI75 at Week 16, are to be evaluated hierarchically testing both hypotheses of no difference between active and placebo at the 5% significance level. The hypothesis for IGA 0/1 will be tested first; if significant, the EASI75 hypothesis will be tested.

The null hypothesis for the first primary endpoint is that there is no difference at Week 16 in obtaining IGA 0/1 between tralokinumab+TCS and placebo+TCS. The null hypothesis for the second primary endpoint is that there is no difference at Week 16 in obtaining EASI75 between tralokinumab+TCS and placebo+TCS. Each hypothesis will be tested against the 2-sided alternative that there is a difference between the 2 treatment groups.

For the single endpoint IGA 0/1 at Week 16, a sample size of 369 subjects randomised 2:1 will provide 90% power to detect a difference between the 2 arms, assuming response rates of 30% for tralokinumab+TCS and 15% for placebo+TCS. For the single endpoint EASI75 at Week 16, a sample size of 369 will provide a nominal power >99.9% to detect a difference between tralokinumab+TCS and placebo+TCS, assuming EASI75 response rates of 40% and 15%, respectively. The combined power for demonstrating a significant difference for both endpoints is therefore effectively also 90% with a sample size of 369 subjects, even when assuming no correlation between the 2 primary endpoints. In all cases, the evaluations will be made with a 2-sided 5% significance level.

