12.3.12 General principles

Unless otherwise stated, all significance tests will be two-sided using the 5% significance level. All CIs will be presented with 95% degree of confidence.

An observed-cases approach will be used for tabulations of data by visit (i.e. involving only those subjects who attended each specific visit).

Categorical data will be summarised using the number and percentage of subjects in each category and treatment group. Continuous data will be summarised using the mean, median, standard deviation, minimum and maximum values.

All the analyses specified in the protocol will be reviewed in relation to the blinded data actually obtained and the statistical analysis plan update will be finalised before breaking the randomisation code.

Any changes from the statistical analysis planned in this clinical trial protocol will be described and justified in a protocol amendment, the statistical analysis plan update and/or in the CTR dependent on the type of deviation.

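### The only stated between-arm comparison of adverse events is a 5%-level chi-square or Fisher test without a risk difference or confidence interval, which is uninformative for uncommon events

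*Protocol*

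**What the plan says.** Section 12.3.9.1 makes the frequency of AEs and SAEs an additional secondary endpoint. Two sentences define how the arms are compared:

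- For adverse events: "The percentage of subjects with AEs in the initial treatment period will be compared between treatment groups by a chi-square test", with Fisher's exact test when an expected cell count is below 5.
- For events judged related: "The percentage of subjects with related AEs in the initial treatment period will be compared between treatment groups by a chi-square test", with the same fallback.

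The level comes from section 12.3.12: "Unless otherwise stated, all significance tests will be two-sided using the 5% significance level". No stratification, effect measure or interval is named for either comparison.

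The rest of section 12.3.9.1 is descriptive. It plans an overall summary with numbers and percentages, counts by event type, severity and causality by arm, a narrative for each SAE, and tables and listings of AESIs and of events leading to withdrawal or discontinuation. No test is named for SAEs or AESIs.

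Other comparisons in the protocol are specified differently. Section 12.3.5.1 asks for the treatment estimate with its 95% CI for the primary endpoints. Section 12.3.8.1 asks for nominal p-values together with 95% CIs at each visit. Section 12.3.8.2 attaches 95% CIs to the mean number of days with little or no bother.

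**The concern.** A safety comparison should show how large an excess the data leave open. A p-value does not show that, and a trial sized on efficacy can easily return p>0.05 when an uncommon event has doubled. A reader shown only the planned test result beside two percentages could take it as reassurance. The interval would show that a clinically relevant excess has not been excluded.

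The protocol is also uneven here. An exploratory diary measure gets intervals, and the visit-wise p-values are labelled nominal. The AE endpoint gets a bare test under the general 5% rule.

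**Working it through.** **Inputs.** Section 12.1 gives 246 subjects on tralokinumab+TCS and 123 on placebo+TCS. The level is two-sided 5% (sections 12.1 and 12.3.12). The protocol gives no AE rates, so the rates below are assumptions, shown over a range. The safety analysis set is taken as all randomised subjects; it may be slightly smaller.

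**Step 1: reproduce the plan's own power.** Section 12.1 states 90% for IGA 0/1, "assuming response rates of 30% for tralokinumab+TCS and 15% for placebo+TCS". The normal approximation is

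power = Φ[(d − 1.96·SE0)/SE1], with SE0 = √{p̄(1−p̄)(1/246+1/123)} and SE1 = √{pT(1−pT)/246 + pC(1−pC)/123}.

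Here d = 0.15 and p̄ = (2×0.30+0.15)/3 = 0.25, so SE0 = 0.0478 and SE1 = 0.0435. Power = Φ(1.294) = 0.902, which agrees with the stated 90%.

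**Step 2: power of the AE test as written.** For each pair of rates, the binomial probabilities of all tables in which the protocol's rule rejects were summed. The rule is uncorrected chi-square, or Fisher's exact test if an expected count is below 5.

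| Placebo rate | Tralokinumab rate | Power |
|---|---|---|
| 1% | 2% | 2% |
| 2% | 4% | 11% |
| 3% | 6% | 20% |
| 5% | 10% | 37% |
| 10% | 20% | 71% |
| 5% | 15% | 86% |
| 15% | 30% | 90% |
| 60% | 70% | 48% |
| 60% | 75% | 84% |

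The normal approximation gives 0.213 for 6% v 3% and 0.360 for 10% v 5%, in line with the enumeration. At the placebo rates of 1% to 5% tabulated here, a doubling is missed about 63% to 98% of the time.

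**Step 3: what an interval would show.** Take 24/246 v 6/123, that is 9.8% v 4.9%, a difference of 4.9 points.

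- Chi-square: the pooled rate is 30/369 = 0.0813 and the smallest expected count is 30×123/369 = 10, so chi-square applies. SE0 = √(0.0813×0.9187×0.012195) = 0.0302, z = 0.0488/0.0302 = 1.62, p = 0.11.
- Wilson limits: 0.0664 to 0.1411 for tralokinumab and 0.0225 to 0.1023 for placebo.
- Newcombe lower limit: 0.0488 − √{(0.0976−0.0664)² + (0.1023−0.0488)²} = −0.013.
- Newcombe upper limit: 0.0488 + √{(0.1411−0.0976)² + (0.0488−0.0225)²} = +0.100.

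Other illustrative outcomes, computed the same way:

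| Tralokinumab | Placebo | Difference (points) | 95% CI | p |
|---|---|---|---|---|
| 8/246 | 1/123 | +2.4 | −1.5 to 5.5 | 0.28 (Fisher) |
| 12/246 | 3/123 | +2.4 | −2.5 to 6.2 | 0.26 |
| 40/246 | 12/123 | +6.5 | −1.2 to 13.1 | 0.09 |
| 165/246 | 74/123 | +6.9 | −3.3 to 17.4 | 0.19 |

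Every one is non-significant, and the upper limits range from 5.5 to 17.4 points.

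**The case against.** The strongest reply has four parts.

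- **The tests are not the only AE output.** A reader might infer that harm is judged by p-values alone. The documents do not support that: numbers, percentages, severity, causality, SAE narratives and AESI tables are all planned, and SAEs and AESIs have no test at all. Anyone with the counts can work out an interval. This stands, but it leaves the reader to do so for a named endpoint.
- **Nothing depends on the AE tests.** They lie outside the testing hierarchy of section 12.3.4, and no section sets a safety decision on p>0.05 or says that non-significance will be read as absence of harm. This stands. The risk is misreading by others, not a stated rule.
- **Low power is not general.** It is tempting to say that a non-significant result tells us almost nothing about harm. That fails for large differences, where power is 71% to 90% (20% v 10%, 15% v 5%, 30% v 15%, 75% v 60%). Section 12.3.9.1 also leaves unclear whether the test covers any AE or each event type. If it covers any AE, rates of 3% to 10% are not the natural illustration. Yet 70% v 60% still has only 48% power, and the last outcome in the second table is non-significant with an upper limit of 17.4 points.
- **Effect measures for AE tables are commonly left to the statistical analysis plan.** That document was not available and may already add intervals, and naming a test does not forbid them. But here the protocol did not stay silent. It fixed the method, and fixed it differently from its other comparisons.

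A reader might also see the unstratified test as biased, because randomisation is stratified by region and baseline IGA. It is not: section 9.2 keeps allocation at 2:1 within the strata, so the crude difference is not systematically distorted.

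**Conclusion.** The point holds as a modest but worthwhile correction. Section 12.3.9.1 fixes a significance test, without an effect size or interval, as the only stated comparison of AEs and related AEs between arms. For uncommon events at 246 v 123 that test is uninformative: about 20% power for 6% v 3% and 37% for 10% v 5%. A non-significant result can sit beside an interval reaching about +10 points.

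These figures rest on assumed event rates and on a safety set equal to the randomised numbers. The conclusion does not extend to large differences, does not imply bias from the missing stratification, and does not mean that the sponsor plans to read p>0.05 as safety.

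**What to change.** In section 12.3.9.1, for the initial treatment period:

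- Present the risk difference (tralokinumab+TCS minus placebo+TCS) with a 95% CI for any AE, SAEs, related AEs, AESIs and the more frequent preferred terms.
- Stratify by region and baseline IGA where counts allow; otherwise use an unstratified score-type interval such as Newcombe's.
- Label any p-values kept as nominal and descriptive, and say whether they apply overall or per event type.

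The cost is a few sentences and extra table columns from data already collected. Sample size, visits and the efficacy alpha are unaffected. The small downside is many intervals without multiplicity control, which the descriptive label should make plain.

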12.3.9.2 Vital signs

The change in vital signs (blood pressure, heart rate, body temperature) from baseline to each visit will be summarised by visit and treatment group as mean, standard deviation, median, minimum and maximum values for the safety analysis set and the continuation treatment safety analysis set.

12.3.9.3 Clinical laboratory evaluation

The change in each of the laboratory parameters from baseline to each visit will be summarised by visit and treatment group as mean, standard deviation, median, minimum and maximum values for the safety analysis set and the continuation treatment safety analysis set.

Laboratory parameters will be classified as 'low', 'normal' or 'high', depending on whether the value is below, within or above the reference range, respectively. A shift table will be produced showing the categories at baseline against those at end of treatment. Subjects with laboratory parameters outside the reference range will be listed.

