7.1 Overall trial design

Overview

This is a randomised, double-blinded, placebo-controlled phase 3 trial to confirm the efficacy and safety of tralokinumab administered on a background of TCS therapy in adult subjects with moderate-to-severe AD. The trial will consist of a screening period of 2 to 6 weeks (Weeks -6/-2 to 0), an initial treatment period of 16 weeks (Weeks 0 to 16), and a continuation treatment period of 16 weeks (Weeks 16 to 32). The primary endpoints are assessed at Week 16, and the final efficacy assessment will be performed at Week 32. An off-treatment follow-up period for the assessment of safety is also included (Weeks 32 to 46). A schematic of the trial design is provided in Panel 1.

Screening period (Week -6 to Week 0)

The screening period has a minimum duration of 2 weeks and a maximum duration of 6 weeks and includes 1 or 2 screening visits. The exact duration of the screening period for

Trial ID: LP0162-1339	Date: 29-Aug-2018	Version: 4.0
		Page 35 of 129

the individual subject depends on the length of any washout period needed, as specified in the exclusion criteria in Section 8.3 (i.e. 4 weeks prior to randomisation for systemic immunosuppressive/immunomodulating drugs, systemic corticosteroid use, or three or more bleach baths during any week within the 4 weeks; 2 weeks prior to randomisation for TCSs, TCIs, or topical phosphodiesterase 4 [PDE-4] inhibitors). If no washout or a 2-week washout period is required, screening will be reduced to 2 weeks and reduced to 1 visit (Week -2; visit 2), i.e., the 2 screening visits will be merged. Eligibility will be assessed at the (first) screening visit and on Day 0 (hereinafter "baseline") prior to randomisation.

All subjects will attend a screening visit 14 days before baseline (Week -2; visit 2) where they will receive electronic diary (eDiary) training and start the eDiary. Data entered into the eDiary during the 2 weeks before randomisation (including the data collected on the day of the baseline visit [visit 3]) will be used to calculate baseline values of the patient-reported outcomes (PROs).

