Subjects randomised to placebo in the initial treatment period and with a clinical response at Week 16 will continue to receive placebo Q2W in the continuation treatment period.

Subjects randomised to tralokinumab or placebo in the initial treatment period who do not fulfil either of the criteria for clinical response at Week 16 will receive tralokinumab Q2W in the continuation treatment period.

All subjects will stay on the TCS regimen during the continuation treatment period.

Safety follow-up period (Week 32 to Week 46)

Subjects, except those who enter the long-term extension trial (LP0162-1337, ECZTEND, see below), will complete a 14-week off-treatment follow-up period for the assessment of safety, PK, and anti-drug antibodies (ADA).

Long-term extension trial (selected countries)

Eligible subjects may be invited to enter a long-term extension trial conducted under a separate protocol (LP0162-1337, ECZTEND). Subjects who transfer to ECZTEND must have had their last visit in the treatment period (Week 32 under the current protocol).

Trial ID: LP0162-1339	Date: 29-Aug-2018	Version: 4.0
		Page 37 of 129

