9.1.3 Administration of trial products

9.1.3.1 Administration of IMP

The IWRS will assign the required IMP kit numbers for each subject at each dispensing visit.

The first day of dosing is considered Day 0 (visit 3). Each subject will receive 4 SC injections (each 1.0 mL) of 150 mg tralokinumab or placebo to receive a total loading dose of 600 mg tralokinumab or placebo.

At subsequent visits in the initial treatment period, each subject will receive 2 SC injections (each 1.0 mL) of 150 mg tralokinumab or placebo to receive a total dose of 300 mg tralokinumab or placebo (Q2W).

Subjects in the continuation treatment period will receive either:

- Tralokinumab Q2W (2 SC injections [each 1.0 mL] of 150 mg tralokinumab).
- Tralokinumab Q4W (alternating dose administrations of 2 SC injections [each 1.0 mL] of 150 mg tralokinumab and placebo).
- Placebo Q2W (2 SC injections [each 1.0 mL] of placebo)

Dosing visits are shown in the schedule of procedures (Section 4). The last administration of IMP will occur at Week 30.

IMP will be administered by a qualified, unblinded healthcare professional (HCP; see Section 9.2.1 for blinding details). A minimum interval of 7 days is required between 2 dosing visits.

Trial ID: LP0162-1339	Date: 29-Aug-2018	Version: 4.0
		Page 49 of 129

The injections will be administered into the SC tissue of the upper arm, anterior thigh, or abdomen, separated by at least 3 cm. The injection site must be recorded in the source documents at each treatment visit and recorded in the eCRF.

Further details on IMP administration are provided in a drug handling manual. IMP administration must be carried out according to these instructions.

After IMP administration

For the first 3 IMP dosing visits in both the initial treatment period (i.e., Weeks 0, 2, and 4) and after re-randomisation (i.e. Weeks 16, 18, and 20), subjects will be monitored after IMP administration for immediate drug reactions for a minimum of 30 minutes with vital signs taken at 30 minutes or until stable, whichever is later. Vital signs will be documented in the eCRF.

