12.2 Trial analysis sets

All screened subjects will be accounted for in the CTR.

All subjects randomised to initial treatment are included in the full analysis set and will be analysed for efficacy up to Week 16. Exclusions from the full analysis set can be considered in special cases as described in ICH E9, Section 5.2.1, Full Analysis Set. If it is decided to exclude a randomised subject from the full analysis set, a justification addressing ICH E9 will be given.

A per protocol analysis set will be used as an efficacy subset for the analysis of the primary endpoints up to Week 16, and analyses based on the per protocol analysis set will be

Trial ID: LP0162-1339	Date: 29-Aug-2018	Version: 4.0
		Page 84 of 129

performed to support the results obtained for the full analysis set. The per protocol analysis set will be defined by excluding subjects from the full analysis set for whom any of the following conditions apply:

- receive no treatment with the IMP.
- provide no assessment of IGA or EASI following start of treatment.
- are known to have taken the wrong IMP throughout the initial treatment period of the trial.
- do not fulfil the inclusion criteria no. 3, 6, 7, and 8.

A safety analysis set will be defined by excluding subjects from the full analysis set who either received no treatment with IMP and/or for whom no post-baseline safety data are available.

A continuation treatment analysis set will be defined as subjects in the full analysis set who have not withdrawn from trial prior to or at the Week 16 visit (visit 11).

A continuation treatment safety analysis set will be defined as subjects who are exposed to IMP at or after the Week 16 visit (visit 11).

Based on the above-mentioned rules, the inclusion/exclusion of subjects from the trial analysis sets will be documented in the statistical analysis plan update before breaking the randomisation code.

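### For placebo subjects who start tralokinumab at Week 16, continuation-period laboratory and vital-sign changes run from Day 0 and so do not show change since starting the drug

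*Protocol*

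**What the plan says.** Section 7.1 has eligibility assessed at screening and again "on Day 0 (hereinafter 'baseline') prior to randomisation", which fixes the meaning of baseline. Section 12.3.9.2 then states: "The change in vital signs (blood pressure, heart rate, body temperature) from baseline to each visit will be summarised by visit and treatment group". The same sentence goes on to give the statistics, ending with "minimum and maximum values for the safety analysis set and the continuation treatment safety analysis set". Section 12.3.9.3 uses the same construction for laboratory values ("The change in each of the laboratory parameters from baseline to each visit will be" summarised, for the same two sets) and adds: "A shift table will be produced showing the categories at baseline against those at end of treatment". Neither section names a second reference value for the continuation period.

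Section 12.2 defines the continuation treatment safety analysis set as "subjects who are exposed to IMP at or after the Week 16 visit (visit 11"), so former placebo subjects are in it. Under Section 7.1, subjects from either arm without a clinical response at Week 16 "will receive tralokinumab Q2W in the continuation treatment period". Section 9.1.3.1 ("Subjects in the continuation treatment period will receive either") lists three regimens: tralokinumab Q2W, tralokinumab Q4W and placebo Q2W. Section 12.3.9 has safety reported separately for the two periods.

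**The concern.** In the initial period, and for anyone on tralokinumab since Day 0, the Day 0 value is the right reference. For a placebo non-responder it is not the last value before the drug. At every continuation visit, that subject's change from Day 0 is the change over 16 weeks of placebo+TCS plus the change since the first tralokinumab dose. The tables cannot separate the two parts, so a shift that begins with tralokinumab could be hidden or imitated by what happened earlier.

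IgE illustrates this. It is a scheduled laboratory parameter; Section 5.1 says IL-13 drives IgE production, and Section 5.2 says tralokinumab blocks IL-13. At Week 20 a switched subject has had 4 weeks of tralokinumab, but the tabulated change covers 20 weeks.

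Assessing safety over 32 weeks is a stated objective (Panel 4), and the continuation tables are reported separately. What is at stake is whether they show what happens to these measures when the drug is started.

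**Working it through.** **Is there a pre-tralokinumab value?** Panel 2 schedules serum chemistry, haematology, IgE, urinalysis and vital signs at Week 16. Section 10.1 places safety and laboratory assessments before administration of IMP. A pre-dose Week 16 value is therefore planned.

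**Inputs**
- Arms: 246 tralokinumab, 123 placebo (Sections 7.2 and 12.1).
- About 40% of tralokinumab subjects re-randomised 1:1 to Q2W or Q4W (Section 7.2).
- Placebo response rates: IGA 0/1 15%, EASI75 15% (Section 12.1).
- Clinical response means either criterion (Section 7.1). The placebo response rate is therefore 15% if the two overlap fully and 30% if they do not overlap at all.

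**The plan's own figures.** The protocol gives no figure for this point. The response rates used here come from the power statement, which reproduces with the usual two-proportion normal approximation.
- IGA 0/1, 30% versus 15%: pooled rate (246×0.30 + 123×0.15)/369 = 0.25. Standard error under the null: √(0.25×0.75×(1/246 + 1/123)) = 0.0478. Under the alternative: √(0.30×0.70/246 + 0.15×0.85/123) = 0.0435. z = (0.15 − 1.96×0.0478)/0.0435 = 1.29, giving power 0.902 against the stated 90%.
- EASI75, 40% versus 15%: the same formula gives 0.9996 against the stated >99.9%.

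**Subjects who switch from placebo to tralokinumab (before dropout)**
- 123 × (1 − 0.15) = 104.6, about 105.
- 123 × (1 − 0.30) = 86.1, about 86.

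**Their share of the Q2W regimen, if columns are pooled by regimen**
- Tralokinumab responders to Q2W: 246 × 0.40 / 2 = 49.2.
- Tralokinumab non-responders to Q2W: 246 × 0.60 = 147.6.
- Placebo response 15%: 104.6 / (49.2 + 147.6 + 104.6) = 104.6 / 301.4 = 34.7%.
- Placebo response 30%: 86.1 / (49.2 + 147.6 + 86.1) = 86.1 / 282.9 = 30.4%.

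**With withdrawals before Week 16.** The protocol gives no rates, so these are assumptions (tralokinumab versus placebo).

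| Withdrawal | Placebo response 15% | Placebo response 30% |
|---|---|---|
| none | 34.7% | 30.4% |
| 5% vs 15% | 88.9 / 275.8 = 32.2% | 73.2 / 260.1 = 28.1% |
| 10% vs 20% | 83.6 / 260.8 = 32.1% | 68.9 / 246.0 = 28.0% |

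**Placebo part of the interval for a switched subject**
- First continuation laboratory visit, Week 20: 16/20 = 80%.
- End of treatment, Week 32: 16/32 = 50%.

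These are shares of time, not of any laboratory change.

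**The case against.** The strongest objection is that Sections 12.3.9.2 and 12.3.9.3 say only that results are shown by treatment group. They do not say that former placebo and former tralokinumab subjects share a column. The regimen list in Section 9.1.3.1 describes dosing, and the wording in Section 12.3.7 about continuation-period treatment groups concerns efficacy. This stands. A reader might infer that a third of the Q2W column is mixed with placebo time; that is conditional on pooling by regimen. The point about the reference value does not depend on pooling, because even in a separate column a change from Day 0 includes the placebo weeks.

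A second objection is that table layout is normally left to the SAP, and Section 12.3.12 provides for a statistical analysis plan update before unblinding. That is fair for layout. But the protocol itself fixes the reference value, and applies it to the continuation set by name.

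Third, a reader might infer that the before/after information is lost, or that the protocol attributes placebo-period changes to tralokinumab. Neither is supported. The Week 16 and later values are collected, and only the within-subject summary from the start of the drug is absent from the planned tables. A change labelled as from baseline describes itself correctly.

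Fourth, the documents show no laboratory parameter moving on placebo+TCS, so no bias can be sized. A before/after change in switched subjects would also be uncontrolled and selected on non-response. Out-of-range laboratory values are listed, and clinically significant findings are reported as adverse events. All of this stands and limits the weight of the point.

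**Conclusion.** The point holds as a cheap improvement. On the protocol's text, continuation-period laboratory and vital-sign changes, and the shift table, use Day 0 for everyone. For about 86 to 105 placebo non-responders (before dropout) they therefore do not show change since starting tralokinumab. That count rests on the 15% placebo rates in Section 12.1 and on an overlap between the two response criteria anywhere from none to complete.

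The share of 28% to 35% of the Q2W column holds only if safety columns are pooled by regimen. It also rests on the 40% re-randomisation figure and, at its lower end, on assumed withdrawals.

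The affected outputs are descriptive. The multiplicity procedure, the efficacy analyses and the randomised Week 0 to 16 safety comparison are untouched. The protocol already applies the relevant principle elsewhere: Section 12.3.3.1 removes placebo periods when summarising tralokinumab exposure.

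**What to change.** In the continuation-period laboratory and vital-sign tables and in the shift table, show subjects switched from placebo to tralokinumab in their own column. Use as their reference the last value before first tralokinumab, that is, the Week 16 pre-dose value. For vital signs, specify pre-dose explicitly, because Section 9.1.3.1 also calls for a reading 30 minutes after dosing at Week 16. Keep Day 0 for the initial-period tables and for subjects on tralokinumab since Day 0, and state in the table titles or footnotes which reference applies.

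The cost is one extra column, a second reference value and a few lines in the statistical analysis plan update. No new data are needed.
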